### **Secondary endpoints**

- Cumulative recurrence -free rate of primary high grade strictures within 12 months
- Change in symptoms as assessed by the Amsterdam cholestatic complaints score (ACCS)(19)
- Clinical success is defined by improvement in liver function tests (LFT) by 20% at week 2 and week 12.
- Improvement in quality of life as assessed by the Short form-36 (SF-36).
- Mortality, morbidity, local complications, stricture recurrence, decompensation of liver disease, liver transplantation over 12 months.

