#### **Sample size**

A prospective study (15) demonstrated a re-intervention free rate of 55% at 12 months for balloon dilatation. Assuming the re-intervention free survival rate at 12 months would be 55% for balloon dilatation (Group B) vs 15% for short term stenting with a biodegradable stent (Group A) yielded a sample size of  $n = 21$  per group. Allowing for a drop out rate of 15%, rendered a total sample size of 50 to attain a power of 80% and a 2-sided alpha level of 0.05. An interim analysis is planned when 50% of the intended total number of study subjects had passed their 3-month visit. We aim to enroll 21 prospective patients into Group A and use a historical cohort for Group B (undergone balloon dilatation in the last 5 years at King's College Hospital). A sample size of 21 was calculated (confidence 0.90, probability 0.1).

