A high grade stricture is defined as a biliary stricture on MRCP with > 75% reduction of the duct diameter in the common bile duct or hepatic ducts. A relevant stricture is a high-grade biliary stricture on imaging in the common bile duct or hepatic ducts with signs or symptoms of obstructive cholestasis (rise in liver bloods tests, itch) and/or bacterial cholangitis.

All ERC and stent insertion attempts are to be carried out by an experienced operator. All procedures are to be carried out under general anaesthetic as per unit protocol. Medium degradation stents only to be used. All patients will receive intravenous Tazocin 4.5g pre/peri-procedure followed by 2 doses after. In the event of a penicillin allergy, intravenous Ciprofloxacin 500mg will be given with 2 further doses post procedure. All patients will be considered for pre/peri-procedural NSAID.

Patient information and informed consent will be obtained at ERC preassessment alongside physical examination and liver biochemistry. Insertion of the stent via ERC with endoscopist questionnaire on ease of placement, visibility on fluoroscopy, the maximum diameter of the stricture, whether dilatation was used and any procedure-related complications. Patient follow up on day one post insertion with questionnaires with a structured interview to assess for procedure-related symptoms and post-insertion AE. Liver function tests and telephone consultation on week 2 (up to 14 days post procedure) to assess for stent degradation, clinical response to therapy, complications and morbidity. MRCP at week 52 to assess for stricture remodelling with improvement in liver biochemistry. Patients will be closely monitored with access to the clinical team involved in the study. The pilot study will be carried out over 24 months.

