**Exclusion criteria**

- Prior stenting or balloon dilatation within the previous 4 months
- Signs of bacterial cholangitis as defined by definite cholangitis according to the criteria in Supp Table 2 (Poinesen et al, Gastro 2015)
- Change of UDCA therapy within 4 weeks
- Inability to give informed consent
- Biliary cirrhosis with Child Pugh score  $\geq 8$
- Estimated transplant free survival < 2 years as calculated by Mayo score > 2
- Suspicion of cholangiocarcinoma, reflected by an imaging study suggestive of metastasis, MRCP with mass lesion with contrast enhancement, or rise in CA19.9 of > 63 U/ml in the previous 4 months together with an absolute value > 130 U/ml
- Signs of current malignancy other than basal cell carcinoma
- Life expectancy < 24 months
- Women pregnant at the time of screening
- HIV or acute or chronic hepatitis B or hepatitis C or substance (drug or alcohol) misuse within the previous 2 years.

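### Historical Group B is defined only by procedure, centre and a 5-year window, without Group A's entry criteria, so the sized comparison is open to selection bias

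*Protocol*

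**What the plan says.** Under Study design the Protocol describes a single-group pilot, but the research hypothesis in section 2 is comparative: fewer interventions than with balloon dilatation alone. The Sample size section calculates 21 per group from assumed 12-month re-intervention-free rates of 55% (dilatation, Group B) and 15% (stent, Group A), with 80% power and two-sided alpha 0.05. It continues: "Allowing for a drop out rate of 15%, rendered a total sample size of 50". For recruitment it says "We aim to enroll 21 prospective patients into Group A" and, for the comparator, "use a historical cohort for Group B (undergone balloon dilatation in the last 5 years" at the same centre). No size, index procedure, selection rule or follow-up is given for Group B.

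For stented patients the requirements are spread over three places in section 3:
- Participants: PSC, stricture narrowing above 75% on MRCP with duct dilatation, no decompensation, and one of five criteria sets, each of which requires raised bilirubin and/or ALP.
- Exclusion criteria: "Prior stenting or balloon dilatation within the previous 4 months", definite cholangitis, Child-Pugh score of 8 or more, Mayo score above 2, suspected cholangiocarcinoma, and others.
- Interventions: a stricture judged at ERCP to be suitable for either treatment, and withdrawal if cytology shows cholangiocarcinoma or high-grade dysplasia.

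Follow-up of stented patients includes "MRCP at week 52 to assess for stricture remodelling with improvement in liver biochemistry". The first secondary endpoint is "Cumulative recurrence -free rate of primary high grade strictures within 12 months".

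**The concern.** Group B carries the research hypothesis and the only powered comparison, yet as written it is a different population from Group A. Taken literally, its definition does not even require PSC. It could admit patients dilated repeatedly at short intervals, decompensated patients, or patients in whom malignancy was already suspected. It could equally admit patients with milder strictures and near-normal liver tests. A difference in re-intervention between the groups could then reflect who was selected rather than what was done to them.

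A secondary point concerns outcome ascertainment. A high-grade stricture is defined on MRCP, and only Group A has a protocol MRCP at week 52. If the recurrence-free rate is also compared between groups, recurrence in Group B would be seen only where imaging happened to be done.

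**Working it through.** **1. The Protocol's own figure.** Inputs from the Sample size section: 55% and 15%, power 80%, two-sided alpha 0.05. Pooled-variance formula with mean rate 0.35:

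n = [1.96·√(2·0.35·0.65) + 0.842·√(0.55·0.45 + 0.15·0.85)]² / 0.40² = 21.1, which rounds up to 22. The arcsine formula gives 20.5, which rounds up to 21. For the total, 42/0.85 = 49.4, so 50.

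The stated 21 per group and 50 in total are reproduced to within one patient per group. The calculation makes no allowance for a non-randomised comparator. (As printed, the two rates put the stent below dilatation, opposite to the hypothesis. That is a separate matter and does not affect this point.)

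**2. Entry conditions side by side.**

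| Condition | Group A | Group B |
|---|---|---|
| PSC | required | not stated |
| Stricture above 75% on MRCP | required | not stated |
| Raised bilirubin and/or ALP | required | not stated |
| No decompensation | required | not stated |
| No stenting or dilatation in prior 4 months | required | not stated |
| Child-Pugh and Mayo limits | required | not stated |
| No definite cholangitis or suspected cholangiocarcinoma | required | not stated |
| Suitable for both treatments at ERCP | required | not stated |
| Centre and period | single centre, prospective | same centre, last 5 years |

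Some of these conditions keep sicker or recently treated patients out of Group A. Others (stricture grade, raised liver tests) keep milder patients out. Leaving both kinds off Group B means that selection can act in either direction.

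**3. What a shift would do.** The sizes of shift below are assumptions; none comes from the Protocol. Assume no true treatment effect, a base rate of 55% re-intervention-free, and 21 patients per group. The test is z = (a/21 − b/21)/√(p̄(1−p̄)·2/21), rejecting when |z| > 1.96. Rejection probabilities are summed exactly over all pairs of binomial outcomes.

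If a fraction f of Group B is certain to be re-treated, its rate is 0.55·(1 − f):

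| f | Group B rate | Spurious difference | False-positive rate |
|---|---|---|---|
| 0 | 55% | 0 points | 4.7% |
| 25% | 0.55·0.75 = 41% | 14 points | 13.6% |
| 40% | 0.55·0.60 = 33% | 22 points | 29.3% |

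If Group B instead had milder disease and a higher rate, the error would run against the stent:

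| Group B rate | Spurious difference | False-positive rate |
|---|---|---|
| 65% | 10 points | 10.0% |
| 70% | 15 points | 17.4% |
| 75% | 20 points | 28.5% |

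**4. Would more controls help?** With f = 25% and 100 unrestricted controls against 21 stented patients, the false-positive rate is 21.8%, compared with 13.6% at 21 against 21. A larger ineligible control group estimates the wrong rate more precisely.

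**The case against.** The strongest reply is that this is declared a single-group pilot, and that its primary endpoint, technical success and safety of stent placement, needs no control group. That stands, and it limits the reach of the point. It does not remove the point, because the hypothesis and the sample size both rest on the comparison. Nor can the matter simply be left to a SAP: who the controls are is a design decision that should be fixed before records are selected.

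A reader might infer three stronger things that the document does not support.
- *That the bias favours the stent.* Group A has a severity floor as well as exclusions for advanced disease, and nothing in the Protocol says that the centre runs serial dilatation programmes. Net direction and size cannot be derived.
- *That differential detection spoils the main comparison.* The week-52 MRCP is described as assessing remodelling. It falls at the end of the 12-month window, so it can hardly affect re-intervention-free survival within it. The Protocol also does not say that the recurrence-free rate is compared with Group B. The ascertainment point holds only if that comparison is made.
- *That Group B is limited to 21.* That figure is the calculated requirement per group. Only Group A is given 21 as a recruitment target, and Group B has no stated size or cap.

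It is also fair to say that the flow chart is not shown in the text available, so whether it says anything about Group B could not be checked. Finally, some Group A criteria rest on graded symptom scores that old records may not hold.

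**Conclusion.** The point holds for the between-group comparison and the research hypothesis, and not for the primary endpoint. As written, the Protocol compares patients selected by strict criteria with patients selected only by procedure, centre and period. The comparison is open to selection bias of unknown size and direction, and adding controls does not cure it. It would be too strong to say that the comparison is known to be biased.

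The false-positive rates of 13.6% and 29.3%, against 4.7% with no shift, show scale only. They rest on an assumed 25% or 40% of Group B being certain to be re-treated, a 55% base rate, no true effect and 21 per group. Shifts of similar size in the other direction produce comparable error against the stent.

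**What to change.** 1. Reconcile Group A's own criteria first. The Participants section gives two age rules (18 to 75, and 18 or older) and two stricture rules (a dominant stricture judged functionally relevant, and narrowing above 75% on MRCP). Until these agree, there is no single set to apply to Group B.
2. Define Group B as all consecutive PSC patients at the centre in the 5-year window whose first qualifying balloon dilatation meets Group A's inclusion and exclusion criteria at that procedure, as far as records allow. This includes no stenting or dilatation in the preceding 4 months. State how a missing criterion is handled.
3. Keep re-intervention-free survival at 12 months as the between-group outcome, with one definition of re-intervention applied to the records of both groups.
4. Report the week-52 MRCP findings for Group A descriptively, without a comparison to Group B.

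The cost is Protocol wording and chart review, with no extra enrolment. The downside is a smaller historical pool, and some records will lack a criterion such as the symptom scores.

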#### **Participants**

Eligible patients with a diagnosis of PSC according to the European association for study of liver 2009 criteria, ascertained with MRCP, ERC, percutaneous transhepatic cholangiography and/or liver biopsy were between 18-75 years of age and fulfilled at least 1 of the following 5 criteria sets: (1) serum bilirubin  $> 3$  times the upper limit of normal (ULN); (2) progression of right upper quadrant pain (RUQP), pruritus, fatigue and/or fever attributed to acute bacterial cholangitis by at least 1 grade according to the Amsterdam Cholestatic Complaints score (ACCS) within the last month, together with a 50% increase of total bilirubin and/or ALP within

the last 4 months and absolute value > 1.2 times the ULN; (3) increase of 20% or more of total bilirubin and/or ALP within the last 4 months and absolute value > 1.2 times the ULN, together with a documented dominant appearing stricture on MRCP or ERC < 4 months before screening; (4) progression of RUQP, pruritus, fatigue and/or fever attributed to bacterial cholangitis by at least 1 grade within the last month, together with total bilirubin and/or ALP > 1.2 times the ULN and a documented stricture on recent MRCP or ERC < 4 months before screening; (5) summed cholestatic complaints score of  $\geq 3$ , or pruritus  $\geq 2$ , or RUQP  $\geq 2$  at screening, together with total bilirubin and/or ALP > 1.2 times the ULN and a documented dominant stricture on recent MRCP or ERC < 4 months before screening. A dominant stricture was defined as any stricture arising in the extrahepatic or left/right main ducts that was deemed functionally relevant by the treating endoscopist/radiologist.

All participants will provide written consent. Eligible patients will be:

- Patients with PSC without evidence of decompensation of chronic liver disease (ascites, hepatic encephalopathy).
- Evidence of a high grade stricture (>75% narrowing) on Magnetic resonance cholangiopancreatography (MRCP) with bile duct dilatation with no evidence of decompensation of liver disease and no other possible causes of elevated liver tests.
- Participants will be aged 18 years or older.
- The decision to proceed to an ERC will be in the Liver Xray/autoimmune MDT as per standard of care (SOC).

A high grade stricture is defined as a biliary stricture on MRCP with > 75% reduction of the duct diameter in the common bile duct or hepatic ducts. A relevant stricture is a high-grade biliary stricture on imaging in the common bile duct or hepatic ducts with signs or symptoms of obstructive cholestasis (rise in liver bloods tests, itch) and/or bacterial cholangitis.

All ERC and stent insertion attempts are to be carried out by an experienced operator. All procedures are to be carried out under general anaesthetic as per unit protocol. Medium degradation stents only to be used. All patients will receive intravenous Tazocin 4.5g pre/peri-procedure followed by 2 doses after. In the event of a penicillin allergy, intravenous Ciprofloxacin 500mg will be given with 2 further doses post procedure. All patients will be considered for pre/peri-procedural NSAID.

Patient information and informed consent will be obtained at ERC preassessment alongside physical examination and liver biochemistry. Insertion of the stent via ERC with endoscopist questionnaire on ease of placement, visibility on fluoroscopy, the maximum diameter of the stricture, whether dilatation was used and any procedure-related complications. Patient follow up on day one post insertion with questionnaires with a structured interview to assess for procedure-related symptoms and post-insertion AE. Liver function tests and telephone consultation on week 2 (up to 14 days post procedure) to assess for stent degradation, clinical response to therapy, complications and morbidity. MRCP at week 52 to assess for stricture remodelling with improvement in liver biochemistry. Patients will be closely monitored with access to the clinical team involved in the study. The pilot study will be carried out over 24 months.

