**Interventions**

Eligible patients will undergo ERCP after informed consent. Periprocedural antibiotic prophylaxis will consist of intravenous piperacillin-tazobactam 4.5g or intravenous ciprofloxacin 500mg, and a subsequent dose 6 or 12 hours after.

Patients will be considered for the study only when, in the absence of purelant bile and fever > 38.5°C, 1 or more dominant stricture(s) of the common bile duct, the common hepatic duct and/or main left or right hepatic duct are encountered and deemed amenable to both balloon dilatation or stenting by the endoscopist. Before any intervention where possible, brush cytology will be obtained of any suspicious sominant stricture. If brush cytology demonstrates cholangiocarcinoma or high-grade dysplasia, that patient will be withdrawn from the study. Sphincterotomy will be performed at the discretion of the endoscopist.

[figure not shown]

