### **Stenting**

A 6Fr Archimedes (medium degradation) stent will be used for for strictures at the biliary hilum with consideration of bilateral stents if possible. 8Fr or 10Fr Archimedes (fast degradation) stents will be considered for dominant strictures in the common bile duct. Balloon dilatation (4mm or 6mm diameter) to facilitate stent placement will be allowed. If stent placement proved impossible after 2 ERCPs, then this will be classified as a failure. After the procedure, patients will be kept overnight for observation and intravenous antibiotics.

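### The protocol limits the trial to medium-degradation stents in one place and offers fast-degradation stents for the common bile duct in another; the count of antibiotic doses after the procedure also conflicts

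*Protocol*

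**What the plan says.** **Stent type.** Under Methods, the Participants section sets a general rule: "Medium degradation stents only to be used". The Stenting section gives a rule by site. For the hilum, "A 6Fr Archimedes (medium degradation) stent will be used for for strictures at the biliary hilum". For the common bile duct, "8Fr or 10Fr Archimedes (fast degradation) stents will be considered for dominant strictures in the common bile duct". The Interventions section admits patients in whom "1 or more dominant stricture(s) of the common bile duct, the common hepatic duct and/or main left or right hepatic duct are encountered", so common bile duct strictures are within the trial population.

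**Antibiotics.** Participants states: "All patients will receive intravenous Tazocin 4.5g pre/peri-procedure followed by 2 doses after". For penicillin allergy it says that "intravenous Ciprofloxacin 500mg will be given with 2 further doses post procedure". Interventions describes prophylaxis as "intravenous piperacillin-tazobactam 4.5g or intravenous ciprofloxacin 500mg, and a subsequent dose 6 or 12 hours after". Stenting adds that patients stay overnight for observation and intravenous antibiotics, with no number of doses.

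The primary endpoint is technical success and safety of placing the biodegradable stent. The Sample size section plans 21 prospective patients. Nothing in the protocol says which statement prevails where two differ.

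**The concern.** The stent is what the trial tests, and degradation type is one of its defining properties; the Background itself says that degradation times vary. An operator treating a common bile duct stricture finds one section that rules out fast-degradation stents and another that offers them. If a fast stent is placed successfully, the protocol does not tell the analyst whether to count it as a per-protocol success or as a placement outside the protocol. That bears directly on how the primary endpoint is counted.

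The antibiotic conflict is a lesser matter of the same kind. Safety is part of the primary endpoint, and the Background names cholangitis among the risks of stenting, so the prophylaxis that patients receive should be stated once and in one way.

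An analysis plan cannot settle either point. The permitted device and the prophylaxis are protocol content, and staff act on them at the procedure.

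**Working it through.** No figure in the protocol is disputed here, and the sample size does not depend on this point. The check is a comparison of the sections.

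**Stent type by stricture site**

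| Site | Participants | Stenting | Agreement |
|---|---|---|---|
| Biliary hilum | medium only | 6Fr, medium | yes |
| Common bile duct | medium only | 8Fr or 10Fr, fast, to be considered | no |

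1. The rule in Participants carries the word *only* and names no exception.
2. Stenting labels the hilar stent medium and the common duct stent fast in adjacent sentences. It reads as an intended distinction, not a slip.
3. Interventions makes common bile duct strictures eligible, so the conflict can arise in enrolled patients.
4. If the option under Stenting is used, Participants is breached. If a medium stent is used in the common bile duct, Participants is met and Stenting is not clearly breached, because it says only that fast stents will be considered.

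**Number affected.** Let c be the number of the 21 patients with a common bile duct stricture, and k the number of those who receive a fast stent. Placements in conflict with Participants involve k patients, with 0 ≤ k ≤ c ≤ 21. The protocol gives neither c nor k, so the range cannot be narrowed from the document.

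**Antibiotic doses**

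| Source | Before or during | After | Total |
|---|---|---|---|
| Participants (either drug) | 1 | 2 | 1 + 2 = 3 |
| Interventions (either drug) | 1 | 1 | 1 + 1 = 2 |
| Stenting | – | overnight, no count | not determinable |

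The phrase "a subsequent dose 6 or 12 hours after" is singular, so the alternative of 6 or 12 hours concerns timing and does not turn one dose into two. The two counts differ for both drugs and for every treated patient.

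**What is recorded.** The endoscopist questionnaire described in Participants covers ease of placement, fluoroscopic visibility, stricture diameter, use of dilatation and complications. Degradation type is not among the listed items.

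**The case against.** The strongest reply is that the wording under Stenting is permissive. A team that always used medium stents would satisfy Participants and would not clearly contravene Stenting, so the two sections can be followed together. This is correct, and it limits the point in several ways.

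- A reader might infer that the intervention as a whole is undefined. It is not: the sections agree at the hilum, and the conflict is confined to the permitted type in the common bile duct.
- A reader might infer that every common bile duct patient will be a protocol deviation under one section or the other. Only those who actually receive a fast stent would deviate, and only from Participants. Any specific count would rest on an assumed share of sites that the document does not support.
- A reader might infer that degradation type would be fully confounded with stricture site. That is not established. Common bile duct patients could receive either type, a patient may have more than one stricture, and Stenting does not name a type for every eligible duct. Calibre also differs by site under Stenting, so some mixing of devices would remain even with a single degradation type.
- A reader might infer that the antibiotic conflict adds noise to the primary endpoint. The protocol gives nothing from which to size such an effect. In a single-centre, single-group pilot, conflicting wording does not show that prophylaxis would in fact vary between patients.

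It is also fair to say that the protocol gives no degradation times by type and no reason to expect degradation rate to change the technical success of placement. No bias in the result can be claimed.

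What the objection does not remove is the contradiction itself. An option offered in one section is forbidden in another, and no rule of precedence is given.

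**Conclusion.** The point holds as an internal inconsistency in how the intervention is specified. In the common bile duct, using the stent that Stenting names breaks the rule in Participants, and its status for the primary endpoint is then unclear. The size is k patients, where k is the number of common bile duct patients given a fast stent; it may be 0 and cannot exceed 21. The antibiotic discrepancy (two doses after the procedure against one, plus an uncounted overnight provision) is secondary, but its wording covers all treated patients.

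The conclusion rests on the text alone and on one assumption: that no other trial document fixes which statement prevails. It should be corrected before enrolment continues under this text, because it concerns the device under test and the primary endpoint, and the correction costs almost nothing. This conclusion makes no judgement on which stent type or antibiotic schedule is right.

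**What to change.** 1. Reconcile Participants and Stenting to one statement of the permitted degradation types by stricture site, covering every eligible duct. The clinical team decides the content.
2. Reconcile Participants, Interventions and Stenting to one antibiotic schedule, including what the overnight provision means in doses. Again the clinical team decides.
3. If more than one degradation type remains, record the type and site for each stent, and describe technical success and safety by type. State that type, calibre and site may overlap and cannot be separated in 21 patients, so the table is descriptive only.

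Cost: protocol wording for the first two items. If two types remain, add one recorded field, which could sit in the existing endoscopist questionnaire, and one descriptive table. No change to the sample size is needed.

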## **2. AIMS**

### **Research hypothesis**

The use of biodegradable stents leads to remodelling of high grade strictures in patients with PSC with fewer interventions in comparison to balloon dilation alone with a comparable risk profile to current therapy.

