### **Primary endpoint**

Technical success and safety of biodegradable stent placement at ERC

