### **3. Methods**

#### **Study design**

Single centre, open-label, single group pilot study with a follow up of 12 months.

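### The hypothesis of a comparable risk profile would set adverse events actively sought in stented patients against whatever was charted for the historical balloon-dilatation cohort

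*Protocol*

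**What the plan says.** The Research hypothesis (section 2) is comparative on harms. It expects the stent to achieve remodelling "with fewer interventions in comparison to balloon dilation alone with a comparable risk profile to current therapy".

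The comparator appears under Sample size (section 3): "We aim to enroll 21 prospective patients into Group A and use a historical cohort for Group B". That cohort is drawn from patients at the same hospital who had balloon dilatation over the preceding five years. No other comparison group is described.

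Harm collection for stented patients is set out under Participants. At the procedure the endoscopist completes a questionnaire that covers complications. The next step is "Patient follow up on day one post insertion with questionnaires with a structured interview to assess for procedure-related symptoms and post-insertion AE". In week 2 there is a telephone consultation with liver function tests, which also covers complications and morbidity. Patients are to be closely monitored and have access to the study team.

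For Group B the protocol gives no source of harm data, no time window, and no event definitions shared with Group A.

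**The concern.** How often adverse events are found depends on how hard one looks. A structured interview the day after a procedure, and a scheduled call two weeks later, will bring out pain, transient fever and other self-limiting symptoms that many patients would never report unprompted. A cohort treated before the study cannot be given that interview retrospectively. Its early harms have to come from what was written down at the time.

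If all harms are counted in each group and then compared, part of any difference will be a difference in method. An apparent excess with the stent could be an artefact of better collection. Equally, a real excess could be explained away as better collection. No later analysis can recover Group B events that were never asked about, so the point has to be settled in the way the data are collected and in the wording of the claim.

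This is separate from how stricture recurrence is detected. It concerns adverse events, mostly in the first two weeks.

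**Working it through.** **The plan's own figure.** There is none to reproduce. The protocol states no adverse-event rate and no capture rate for records. Its sample-size calculation concerns re-intervention-free survival and has no bearing on this point.

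**The two groups side by side.**

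| Source of harm information | Group A (stent, prospective) | Group B (balloon, historical) |
|---|---|---|
| At the procedure | Endoscopist questionnaire | Not stated |
| Day 1 | Questionnaires and structured interview | Not stated; a trial interview is impossible afterwards |
| Week 2 | Telephone consultation and liver tests | Not stated; cannot be scheduled afterwards |
| Later | Close monitoring, access to study team | Not stated |

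That Group B depends on records is an inference from its being already treated. The protocol does not say so.

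**Illustration of size.** All rates are assumptions.

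- p = true risk of an adverse event, taken as equal in both groups.
- c = fraction of events that records capture in Group B; capture in Group A is taken as complete.
- Observed risks are p in Group A and p × c in Group B.
- Apparent risk ratio = p / (p × c) = 1/c, whatever the value of p.
- Spurious risk difference = p × (1 − c).

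| c | Risk ratio 1/c | Difference, p = 10% | Difference, p = 20% | Difference, p = 30% |
|---|---|---|---|---|
| 90% | 1.11 | 1 point | 2 points | 3 points |
| 75% | 1.33 | 2.5 points | 5 points | 7.5 points |
| 50% | 2.0 | 5 points | 10 points | 15 points |

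In patients, at p = 20% and assuming 21 per group, Group A would be expected to have 21 × 0.20 = 4.2 patients with an event. Group B would show 21 × 0.20 × 0.75 = 3.15 at 75% capture, or 21 × 0.20 × 0.50 = 2.1 at 50%.

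**Against chance.** With 21 per group and equal risk p, the approximate 95% half-width for the risk difference is 1.96 × √(2p(1 − p)/21):

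- p = 10%: 1.96 × √(0.18/21) = 18 points.
- p = 20%: 1.96 × √(0.32/21) = 24 points.

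The assumed biases are smaller than this, so the data could not separate bias from chance.

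**Chance of a visible excess.** With independent binomial counts, Binomial(21, p) and Binomial(21, p × c), at p = 20% the probability that Group A shows at least three more patients with an event is 17% at full capture, 20% at c = 90%, 28% at c = 75% and 43% at c = 50%. The threshold of three is arbitrary and serves only to give scale.

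**The case against.** The strongest reply is that the protocol never specifies a between-group test of harms. It describes a "Single centre, open-label, single group pilot study with a follow up of 12 months", and Group B is brought in only for re-intervention. The risk clause of the hypothesis refers to current therapy without defining it, and the Background also discusses plastic stents. This stands as a limit on the point: what is exposed is the comparative claim, not a stated test. But the claim is made, and the historical cohort is the only group in the protocol against which it could be examined.

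A reader might infer that the primary endpoint is compromised, since it reads "Technical success and safety of biodegradable stent placement at ERC". The text does not support that. The endpoint describes stented patients alone, and active solicitation improves that estimate.

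A reader might also infer that the overnight stay distorts severity grading, because "After the procedure, patients will be kept overnight for observation and intravenous antibiotics". The protocol states no seriousness or severity rule based on admission, and an overnight stay may have been routine for Group B too. Nothing can be built on it.

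The remaining objections carry weight on size. Serious outcomes such as death or transplantation are likely to be in one hospital's records for either group. The bias runs against the stent, so a finding of comparable risk would be conservative in this respect. A formal test would seldom be misled: at a true risk of 20% and 21 per group, a two-sided Fisher test at 0.05 would falsely show excess harm with the stent about 1.2% of the time at full capture, 3.1% at 75% and 7.8% at 50%.

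A statistical analysis plan could fix windows and tabulation. It could not supply Group B events that were never elicited.

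**Conclusion.** The point holds for the risk clause of the hypothesis and no further. Group A's harms are elicited by interview, questionnaire and telephone. Group B's cannot be, so a comparison of overall harms would be unequal by construction. The effect is concentrated in mild, early events and would tend to count against the stent. The descriptive adverse-event rate in stented patients is sound on this account.

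The size cannot be determined from the protocol. Under equal true risk and complete capture in Group A, risk ratios of 1.11, 1.33 or 2.0 follow from assumed record capture of 90%, 75% or 50%. The conclusion also rests on the inference that Group B's early harms come from routine records. If usual care already included some of the same follow-up, the gap would be smaller. This is a modest weakness that is cheap to repair, and it does not undermine the study's main descriptive result.

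**What to change.** Separate the safety reporting into two parts.

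1. **Compared with Group B.** Restrict the comparison behind the risk claim to events that can be verified in the hospital record, for example pancreatitis, cholangitis, bleeding, perforation, unplanned readmission or further procedure, and death. Abstract them in both groups from the same record sources, with the same definitions and the same windows counted from the index ERC.
2. **Group A only.** Report events elicited by interview, questionnaire or telephone descriptively, and state that they are not compared with Group B.

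Reword the Research hypothesis so that the claim about risk refers to the first part only.

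The cost is protocol wording and one abstraction form applied to both groups' records. No visits, patients or procedures are added. The downside is that mild events leave the comparison, which then rests on fewer events and is less precise; they are still reported for stented patients.
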